Protocol I1F-IN-RHCZ, a 24-Week Multicenter, Open-Label, Single-Arm, Phase 4 Study to Evaluate the Safety of Ixekizumab in Patients with Moderate-to-Severe Plaque Psoriasis and/or Active Psoriatic Arthritis in India, has been amended. The new protocol is indicated by amendment (a) and will be used to conduct the study in place of any preceding version of the protocol.

The following are the overall rationale for the changes made to this protocol:

- To comply with Subject Expert Committee (SEC; Ministry of Health [MoH]) recommendations, and
- To provide more clarity regarding the assessments to be collected and analyzed for the PsA participants who have active plaque psoriasis.

Other minor corrections (spelling errors, grammar corrections, formatting, and so on) and clarifications or semantic changes not affecting content have also been made in the document.

The following table presents the overall changes and rationale for the changes made to this protocol:

Section # and Name	Description of Change	Brief Rationale
Section 1.1 Protocol Synopsis and Section 3 Objectives and Endpoints	Added a note for Other Efficacy Endpoints (PASI 75, 90, 100, PASI change from baseline, sPGA [0, 1] and sPGA [0], and BSA change from baseline) - “For PsA participants with 3% or more body surface area (BSA) of PsO, both PsA and PsO efficacy outcomes will be collected.”	To provide more clarity regarding the assessments to be collected and analyzed for the PsA participants who have active plaque psoriasis.
Section 1.1 Protocol Synopsis, Section 1.2 Schema and Section 4.1 Overall Design	Updated a statement related to study treatment.	To provide clarity that treatment regimen for PsA participants with moderate-to-severe PsO is same as that for participants with PsO.
Section 1.1 Protocol Synopsis,	Updated text regarding PsA participants with moderate-to-severe PsO is	To provide clarity that treatment regimen for PsA participants with

Section # and Name	Description of Change	Brief Rationale
Section 4.2 Scientific Rationale for Study Design, and Section 6.1 Study Intervention(s) administered	same as that for participants with PsO in synopsis and Section 6.1. Also, updated Tables RHCZ.6.1 and RHCZ.6.2 in Section 6.1.	moderate-to-severe PsO is same as that for participants with PsO.
Section 1.3 Schedule of Activities	Added a row for “Substance use (alcohol, caffeine, tobacco use).”	To collect additional participant history information.
Section 1.3 Schedule of Activities	Added “Evaluation for Disease Relapse” and footnote annotation b.	To comply with Subject Expert Committee (SEC; Ministry of Health [MoH]) recommendations, Disease Relapse Evaluation has been included at screening visit.
Section 1.3 Schedule of Activities	Added a footnote annotation “i” to update a note describing requirement of assessments for participants with psoriatic arthritis (PsA).	To provide clarity on what assessments are to be administered to which participants.
Section 1.3 Schedule of Activities	Removed baseline assessment of “Collect, review, and enter data from Study Intervention Administration Log.”	Rectified original protocol typo error.
Section 1.3 Schedule of Activities	Included Week 24 evaluation of active tuberculosis (TB) in patients by QuantiFERON Tuberculosis TB Gold test and chest x-ray.	To comply with SEC (MoH) recommendations, Week 24 evaluation has been included for active tuberculosis by QuantiFERON TB Gold test and chest x-ray at Week 24 of the treatment.
Section 1.3 Schedule of Activities	Modified a general table note at the end of schedule of activities (SoA) table footnote.	To provide more clarity regarding the assessments to be collected and analyzed for the PsA participants who have active plaque psoriasis.
Section 2.1 Study Rationale	Added definition of moderate-to-severe plaque psoriasis.	To clarify original content.

Section # and Name	Description of Change	Brief Rationale
Section 4.1.4 Post-Treatment Follow-Up Period (Period 4)	Timing of follow-up visit, Visit 802 is updated to 8 weeks after Visit 801.	To clarify original content.
Section 8.1 Efficacy Assessment	Updated a statement to mention that PsO outcome will be collected among all the PsA participants with 3% or more BSA of PsO. Added Table RHCZ.8.1 to present clinician and patient assessments for different participants.	To provide clarity on what assessments are to be administered to which participants.
Section 8.1.2 American College of Rheumatology 20, 50, and 70 Responder Index	Included a statement in subsection Patient's Assessment of Pain Visual Analog Scale – "Patient's Assessment of Pain VAS will be administered only to PsA participants. The question related to pain assessment will be included in HAQ-DI assessment."	To clarify original content.

1.1. Synopsis

Protocol Title: A 24-Week Multicenter, Open-Label, Single-Arm, Phase 4 Study to Evaluate the Safety of Ixekizumab in Patients with Moderate-to-Severe Plaque Psoriasis and/or Active Psoriatic Arthritis in India

Brief Title: A study to investigate the safety of ixekizumab in participants aged ≥ 18 years with moderate-to-severe plaque psoriasis and/or active psoriatic arthritis in India

Rationale:

The rationale for this post-approval Phase 4 study is to evaluate the safety and tolerability when ixekizumab is administered to participants in India with moderate-to-severe plaque psoriasis (PsO) and/or active psoriatic arthritis (PsA). This Phase 4 safety study is being performed as per conditional marketing approval from the Central Drugs Standard Control Organization (CDSCO), India. As per permission reference, Lilly has committed to conduct a Phase 4 study with ixekizumab in India. In addition to the established safety profile for adult PsO, and PsA, the safety and tolerability data in Indian population from this study are intended to:

- further support the known safety profile for ixekizumab in adult participants with PsO and PsA, and
- establish a better understanding of the benefit-risk relationship for ixekizumab in participants with PsO and PsA.

Objectives and Endpoints:

Objectives	Endpoints
Primary	

 To assess the type of adverse event (AE) and the proportion of Indian participants with PsO and participants with PsA reporting AEs and serious adverse events (SAEs) occurring within the duration of the study (24 weeks) after being started on ixekizumab 	
 AEs, including SAEs, treatment-emergent adverse events (TEAEs), and adverse events of special interest (AESIs) during the treatment period (Week 0 to Week 24)
Secondary	
Specific to Psoriasis Group	

 To evaluate percentage of participants achieving a $\geq 75\%$ improvement in Psoriasis Area and Severity Index (PASI) 	
 Proportion of participants who achieve the following PASI scores: PASI 75 (defined as 75% improvement from baseline in PASI) at Week 12

 To evaluate percentage of participants with a Static Physician Global Assessment (sPGA) (0,1) 	
 Proportion of participants with an sPGA psoriasis score of 0 or 1 (0, 1) at Week 12
Specific to Psoriatic Arthritis Group	

 To evaluate percentage of participants achieving a 20% improvement in American College of Rheumatology response criteria (ACR20) 	
 Proportion of PsA participants achieving ACR20 at Week 24
CCI	
	

Objectives	Endpoints
[REDACTED]	[REDACTED]

Overall Design:

Study RHCZ is a prospective, multicenter, open-label, single-arm, Phase 4 study with 4 study periods assessing outcomes in terms of AEs and SAEs with ixekizumab when used in participants aged ≥ 18 years for PsO and PsA in an Indian population.

Brief Summary:

The study will consist of 4 periods. The study duration for the 4 study periods are:

- Screening Period (Period 1; 5 to 28 days),
- Induction Dosing Period (Period 2; 12 weeks),
- Maintenance Period (Period 3; 12 weeks), and

- Post-Treatment Follow-Up Period (Period 4; at least 4 weeks after the date of participants' early termination visit [ETV] or last regularly scheduled visit at Week 24).

The following treatment will be assessed in this study for PsO participants with no active PsA and PsA participants who meet criteria for moderate-to-severe PsO (participants with moderate-to-severe plaque psoriasis are defined as those with PASI ≥ 12 , sPGA ≥ 3 , and BSA $\geq 10\%$):

- Ixekizumab: 80-mg subcutaneous (SC) injection
 - At Week 0, 160-mg starting dose (two 80-mg injections), followed by 80 mg every 2 weeks (Q2W) from Weeks 2 through 12, and then followed by 80 mg every 4 weeks (Q4W) thereafter (i.e., at Weeks 16 and 20).

The following treatment will be assessed in this study for PsA participants who do not meet criteria of moderate-to-severe PsO:

- Ixekizumab: 80-mg SC injection
 - At Week 0, 160-mg starting dose (two 80-mg injections), followed by 80 mg Q4W (i.e., at Weeks 4, 8, 12, 16 and 20).

Statistical Analysis:

Adverse events and treatment-emergent adverse events will be summarized and analyzed for the safety population for the combined Period 2 (Induction Dosing Period) and Period 3 (Maintenance Period), including the number and percentage of participants who reported TEAEs, TEAEs by maximum severity, death, SAEs, TEAEs related to study treatment, AEs leading to treatment discontinuation, and TEAEs of special interest.

Efficacy analyses in the secondary objectives specific to PsO and PsA will be conducted on the PsO with no active PsA and active PsA participants with at least 1 dose of study intervention and will be summarized with number of responders, response rate and its corresponding 95% confidence intervals (CIs) using normal approximation.

Number of Participants:

Approximately 250 participants (PsO: 150 participants; PsA: 100 participants) are planned to be enrolled into this study and, assuming discontinuations of approximately 10%, approximately 225 participants should complete the 24-week period of treatment.

Intervention Groups and Duration:

Treatment Group	Starting Dose W0	Dose W2-W10	Dose ^a W12-W20
Ixekizumab for 
 • PsO participants with no active PsA, and • PsA participants who meet criteria for moderate-to-severe PsO. 	Ixekizumab 80 mg 2 × SC (total of 160 mg)	Ixekizumab 80 mg SC Q2W at W2, 4, 6, 8, and 10	Ixekizumab 80 mg SC Q4W at W12, 16, and 20
Ixekizumab for PsA participants who do not meet criteria for moderate-to-severe PsO	Ixekizumab 80 mg 2 × SC (total of 160 mg)	Ixekizumab 80 mg SC Q4W at W4, 8, 12, 16, and 20.	

Abbreviations: PsA = psoriatic arthritis; PsO = psoriasis; Q2W = every 2 weeks; Q4W = every 4 weeks; SC = subcutaneous injection; W = week.

^a No dose is given at W24; therefore, W24 is not included in this table.

Note: When the dosing is scheduled at home (for PsO participants with no active PsA and PsA participants who meet criteria for moderate-to severe PsO: W2, W6, W10, W16, and W20; for PsA participants who do not meet criteria of moderate-to-severe PsO: W16 and W20), the participants or care givers will administer the provided ixekizumab prefilled syringes.

Data Monitoring Committee: No.

1.2. Schema

CCI

1.3. Schedule of Activities (SoA)

Table RHCZ.1.1. Schedule of Activities

	Screening (Period 1)	Induction Dosing (Period 2)				Maintenance (Period 3)		Post Treatment Follow-Up (Period 4)	
		Baseline							As Needed
CRF Visit Number	V1	V2	V3	V4	V5	V6	ETV	V801	V802
Study Week		W0	W4	W8	W12	W24		LV + W4	LV + W8
Study Days	-28 to -5 d	0 d	28 ± 3 d	56 ± 3 d	84 ± 3d	168 ± 5 d		± 4 d	± 4 d
Informed consent	X								
Complete medical history	X								
Demographics ^a	X								
Substance use (alcohol, caffeine, tobacco use)	X								
Electrocardiogram	X								
Evaluation for disease relapse ^b	X								
Physical examination ^c	X								
Weight	X	X				X	X	X	
Height		X							
Body mass index		X							
Inclusion/exclusion criteria ^d	X	X							
Vital signs	X	X				X	X	X	X
Concomitant medications	X	X	X	X	X	X	X	X	X
Review preexisting conditions/AEs	X	X	X	X	X	X	X	X	X
Administer study intervention ^e		X	X	X	X				
Dispense study drug		X	X	X	X				
Study drug compliance ^f		X	X	X	X				
Dispense Study Intervention Administration Log		X	X	X	X				
Collect, review, and enter data from Study Intervention Administration Log			X	X	X	X	X		

Schedule of Activities

	Screening (Period 1)	Induction Dosing (Period 2)				Maintenance (Period 3)		Post Treatment Follow-Up (Period 4)		
		Baseline						As Needed		
CRF Visit Number	V1		V2	V3	V4	V5	V6	ETV	V801	V802
Study Week		W0		W4	W8	W12	W24		LV + W4	LV + W8
Study Days	-28 to -5 d	0 d		28 ± 3 d	56 ± 3 d	84 ± 3d	168 ± 5 d		± 4 d	± 4 d
Efficacy Measures										
Clinician-Rated or -Administered Assessments										
PAS ^{fg}	X	X	X	X	X	X	X			
BSA ^g	X	X	X	X	X	X	X			
sPGA ^g	X	X	X	X	X	X	X			
TJC/SJC (68/66 joints) ^h	X	X	X	X	X	X	X			
PGA Disease Activity VAS ^h		X	X	X	X	X	X			
Patient-Rated Assessments										
Patient Assessment of Pain VAS ⁱ		X	X	X	X	X	X			
Patient Global Assessment Disease Activity VAS		X	X	X	X	X	X			
HAQ-DI ⁱ		X	X	X	X	X	X			
Laboratory Tests										
Chest x-ray (local) ^j	X					X	X			
Administer Mantoux TB test/QuantiFERON®-TB Gold ^k	X					X	X			
HIV/HCV	X									
HBV ^l	X	X			X	X	X		X	
Serum pregnancy test ^m	X									
Urine pregnancy test ⁿ		X	X	X	X	X	X			
Serum chemistry	X	X				X	X	X		

Schedule of Activities

	Screening (Period 1)	Induction Dosing (Period 2)					Maintenance (Period 3)		Post Treatment Follow-Up (Period 4)	
										As needed
		Baseline								
CRF Visit Number	V1	V2	V3	V4	V5	V6	ETV	V801	V802	
Study Week		W0	W4	W8	W12	W24		LV + W4	LV + W8	
Study Days	-28 to -5 d	0 d	28 ± 3 d	56 ± 3 d	84 ± 3d	168 ± 5 d		± 4 d	± 4 d	
Laboratory Tests										
Hematology	X	X	X		X	X	X	X	X	
hs-CRP		X	X	X	X	X	X			
Urinalysis	X	X				X	X			

Abbreviations: AE = adverse event; BSA = body surface area; CRF = case report form; d = day; ETV = early termination visit; HAQ-DI = Health Assessment Questionnaire – Disability Index; HBV = hepatitis B virus; HCV = hepatitis C virus; HIV = human immunodeficiency virus; hs-CRP = high-sensitivity C-reactive protein; LV = last visit; PGA = Physician Global Assessment; PASI = Psoriasis Area and Severity Index; PsA = psoriatic arthritis; SJC = swollen joint count; sPGA = static Physician's Global Assessment; TB = tuberculosis; TJC = tender joint count, V = visit; VAS = visual analog scale; W = week.

- a Includes year of birth, gender, and ethnicity.
- b Subjects will be evaluated for past and present disease relapse by the physician (Section 8.2.4).
- c Complete physical at screening (excluding pelvic, rectal, and breast examinations). Physicals should include symptom-directed physical, as well as an examination of heart, lungs, and abdomen, and visual examination of the skin.
- d Participants who test positive for latent TB at screening may be re-screened following appropriate treatment.
- e See Table RHCZ.6.1. When the dosing is scheduled at home, the participants/care givers will administer the provided ixekizumab prefilled syringes. All participants should remain under observation for at least 1 hour after study intervention administration to monitor safety at Week 0.
- f Designated site personnel will be responsible for handling and dispensing of study intervention (ixekizumab).
- g Administered to PsA participants only at the baseline (W0) visit. For PsO participants with 3% or more BSA of PsO, administered at all study visits.
- h Administered to PsO participants only at the baseline (W0) visit. For PsA participants, administered at all study visits.
- i Administered only to PsA participants. The question related to pain assessment will be included in HAQ-DI assessment.
- j To be performed if not done in the prior 6 months to rule out pulmonary TB provided the x-ray and/or report are available for review.
- k Participants who test positive for latent TB at screening may be re-screened. QuantiFERON® may be performed by a Lilly-designated or local laboratory. See Section 8.2.7 for detailed description of QuantiFERON®-TB Gold . In case of Mantoux TB test, participants will have to come back to the site after 2 days for reading the results.
- l All participants will be tested for HBV at screening. Participant who meet criteria for HBV monitoring (see Section 8.2.8.1) will be identified by the central laboratory at baseline and monitored according to the study schedule.
- m To be performed for females of childbearing potential only. Additional urine pregnancy testing can be performed at the investigator's decision. Participants determined to be pregnant will be discontinued from treatment and will no longer be administered study intervention.

n To be performed for females of childbearing potential only. Participants determined to be pregnant will be discontinued from treatment and will no longer be administered study intervention.

Note: For PsO participants with no active PsA, only PsO efficacy outcomes will be collected. For PsA participants with 3% or more BSA of PsO, both PsA and PsO efficacy outcomes will be collected. For PsA participants with less than 3% BSA of PsO, only PsA efficacy outcomes will be collected. ([Table RHCZ.8.1](#)).

2. Introduction

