- Women who are infertile due to surgical sterilization (hysterectomy, bilateral oophorectomy, or tubal ligation) and congenital anomaly such as Müllerian agenesis.

[3] Have given written informed consent approved by Lilly, or its designee, and the Investigational Review Board (IRB)/ERB governing the site.

[4] Willing to self-administer study intervention.

For PsO Participants

[5] Present with chronic PsO based on a confirmed diagnosis of chronic PsO vulgaris for at least 6 months prior to baseline (Week 0; Visit 2).

[6] Have $\geq 10\%$ BSA of psoriasis at screening (Visit 1) and baseline (Week 0; Visit 2).

[7] Have both an sPGA score of ≥ 3 and PASI score ≥ 12 at screening (Visit 1) and baseline (Week 0; Visit 2).

- [8] Are a candidate for phototherapy and/or systemic therapy.

For PsA Participants

- [9] Have a diagnosis of active PsA for at least 6 months (based on a detailed medical history provided by the patient, and a physical exam by the Study Investigator, and/or other evidence such as that provided by joint x-rays, that establishes a history consistent with a diagnosis of active PsA of at least 6 months' duration) and currently meet the Classification for PsA (CASPAP) criteria (Section 10.6).
- [10] Have active PsA defined as the presence of at least 3/68 tender and at least 3/66 swollen joints, as determined by the Tender and Swollen Joint Count Assessment Form (Section 10.7) at Visit 1 (Screening) and Visit 2 (Week 0, baseline).
- [11] Presence of active PsO or a documented history of psoriasis.

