8.1. Efficacy Assessments

The secondary endpoints for PsO group are:

- Proportion of participants who achieve the following PASI scores: PASI 75 (defined as 75% improvement from baseline in PASI) at Week 12
- Proportion of participants with an sPGA score of 0 or 1 (0, 1) at Week 12.

The secondary endpoints for PsA group are:

- Proportion of PsA participants achieving ACR20 at Week 24.

Exploratory endpoints include, but not limited to, DAS-28-CRP and ACR individual components.

For PsO participant who also meet active PsA definition, both PsA and PsO outcomes will be collected for that participant. Likewise, to fulfill the study objective, PsO outcomes will be collected among all the PsA participants with 3% or more BSA of PsO ([Table RHCZ.8.1](#)).

Table RHCZ.8.1. Efficacy Assessments

Assessments	PsO Participants with No Active PsA	PsA Participants with	
		≥3% BSA of PsO	<3% BSA of PsO
Clinician assessments	
 • PASI • Percentage of BSA - Psoriasis • sPGA • PGA Disease Activity VAS 	
 • TJC/SJC (68/66 joints) • PGA of Disease Activity VAS -Psoriasis • PGA of Disease Activity VAS - PsA • PASI • Percentage of BSA - Psoriasis • sPGA • DAS28 - CRP^a • ACR20/50/70^a 	
 • TJC/SJC (68/66 joints) • PGA of Disease Activity VAS - PsA • DAS28 - CRP^a • ACR20/50/70^a
Patient assessments	
 • Patient's Global Assessment of disease activity VAS - Psoriasis 	
 • HAQ-DI • PsA Pain assessment question included in HAQ-DI • Patient's Global Assessment of Disease Activity VAS - PsA • Patient's Global Assessment of Disease Activity VAS - Psoriasis 	
 • HAQ-DI • PsA Pain assessment question included in HAQ-DI • Patient's Global Assessment of Disease Activity VAS - PsA

Abbreviations: ACR20/50/70 = 20%/50%/70% improvement in American College of Rheumatology response criteria; BSA = body surface area;

CRP = C-reactive protein; DAS28 = Disease Activity Score-28; HAQ-DI = Health Assessment Questionnaire – Disability Index; PASI = Psoriasis Area and Severity Index; hs-CRP = high-sensitivity C-reactive protein; PGA = Physician's Global Assessment; PsA = psoriatic arthritis; PsO = plaque psoriasis; SJC = swollen joint count; sPGA = static Physician's Global Assessment; TJC = tender joint count, V = visit; VAS = visual analog scale.

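### Schedule footnote g limits PASI, BSA and sPGA in PsA participants to Week 0, against the schedule's own note, Section 8.1 and the Week 12 summary in Section 9.5.3(ii); where a site follows it, nonresponder imputation can only lower that summary

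*Protocol*

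**What the plan says.** Footnote g in protocol Section 1.3 is attached to the PASI, BSA and sPGA rows. It begins "Administered to PsA participants only at the baseline (W0) visit. For PsO participants with 3% or more BSA of PsO" and ends by giving that second group the assessments at every study visit. No exception is made for PsA participants with active skin disease.

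Other current passages say something different about the same people:

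- The note closing the same schedule: "For PsA participants with 3% or more BSA of PsO, both PsA and PsO efficacy outcomes will be collected". Below the cut-off, the note says: "For PsA participants with less than 3% BSA of PsO, only PsA efficacy outcomes will be collected".
- Section 8.1: "PsO outcomes will be collected among all the PsA participants with 3% or more BSA of PsO". Table RHCZ.8.1, to which both refer, lists PASI, BSA and sPGA in the column for PsA participants at or above 3% BSA and none of the three in the column below 3%.
- Section 9.5.3(ii) plans Week 12 PASI 75 and sPGA (0,1), each with a 95% confidence interval, in the active PsA mITT population with baseline BSA of psoriasis of at least 3%. Both use nonresponder imputation.
- Section 9.3.1 counts a participant with no response data at the timepoint as a nonresponder.

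For participants enrolled as PsO, inclusion criterion [6] already requires at least 10% "BSA of psoriasis at screening (Visit 1) and baseline (Week 0; Visit 2"), and criterion [7] requires sPGA of at least 3 and PASI of at least 12.

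**The concern.** The schedule is the page that sites work from. As printed, it tells them to stop skin assessments after Week 0 in PsA participants, while the analysis section needs those assessments at Week 12 in the subset with at least 3% BSA. The footnote keeps the Week 0 BSA, so these participants still qualify for the denominator of Section 9.5.3(ii). It removes the Week 12 PASI and sPGA, so they cannot reach the numerator.

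A missed skin assessment cannot be made up later, and no analysis plan can restore it. The reported rate would then depend partly on which line of the schedule a site followed. Clarity about assessments in PsA participants with active plaque psoriasis was one of the two stated reasons for amendment (a), so the footnote works against the amendment's own purpose.

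**Working it through.** **No stated figure to reproduce.** The protocol gives no expected PASI 75 or sPGA rate for PsA participants and no count of those with at least 3% BSA. It says only that about 100 PsA participants are planned (Section 9.7). The check is therefore mainly a comparison of passages.

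**Step 1: the passages side by side, for a PsA participant with at least 3% BSA.**

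| Place | PASI, BSA and sPGA after Week 0 |
|---|---|
| Section 1.3, footnote g, first sentence | No |
| Section 1.3, closing note | Yes, PsO outcomes collected |
| Section 8.1 and Table RHCZ.8.1 | Yes |
| Section 9.5.3(ii) | Needed at Week 12 (PASI and sPGA) |

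**Step 2: the second sentence of footnote g.** A 3% condition separates nobody among PsO participants, who all need at least 10%. It does separate PsA participants, and 3% is the cut-off used for them everywhere else. This points to PsO having been written for PsA. The first sentence still conflicts with the other passages as printed.

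**Step 3: who is caught by a literal reading.** PsA participants with at least 3% BSA who do not also meet criteria [6] and [7], that is:

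- BSA from 3% to below 10%; or
- BSA of 10% or more, but sPGA below 3 or PASI below 12.

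Participants who meet both disease definitions are arguably covered by the second sentence. Section 8.1 says of them: "For PsO participant who also meet active PsA definition, both PsA and PsO outcomes will be collected for that participant".

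**Step 4: direction of the effect.** Let p be the Week 12 response rate in the Section 9.5.3(ii) subset if everyone were assessed. Let f be the share of the subset left unassessed because of footnote g, and q the share who would have responded but are unassessed. Under Section 9.3.1 the reported rate is

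R = p − q, with q ≥ 0, so R ≤ p.

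Since max(0, p + f − 1) ≤ q ≤ min(p, f), R lies between max(0, p − f) and min(p, 1 − f). If f = 0, R = p.

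**Step 5: illustration only.** Neither p nor f is in the documents; every value here is assumed. If missingness is unrelated to response, q = p × f and R = p(1 − f):

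| p | f = 0.10 | f = 0.25 | f = 0.50 |
|---|---|---|---|
| 0.60 | 0.54 | 0.45 | 0.30 |
| 0.75 | 0.675 | 0.5625 | 0.375 |
| 0.90 | 0.81 | 0.675 | 0.45 |

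For p = 0.75 and f = 0.25 the shortfall is 0.75 × 0.25 = 0.1875, about 19 points. Without the unrelated-missingness assumption, R lies between 0.75 − 0.25 = 0.50 and min(0.75, 0.75) = 0.75.

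**Step 6: what is not touched.** Summary (i) covers PsO participants without active PsA, who get all visits under the footnote's second sentence. ACR20 uses joint counts, pain, two global assessments, HAQ-DI and hs-CRP, none of which carries footnote g. The primary analysis is of adverse events. Section 9.1 plans no hypothesis test.

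**The case against.** The strongest reply is that this is a wording slip and not a plan to skip assessments. The sponsor's intention is stated consistently in the closing note, Section 8.1, Table RHCZ.8.1 and Section 9.5.3. A reader who notices that the footnote's second sentence makes no sense for PsO participants finds the right rule in the note under the same schedule. Nothing in the documents shows that any site would prefer the footnote. This stands as a limit on how likely the harm is. It does not remove the contradiction, because the first sentence is clear when read on its own.

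A reader might also infer that the footnote contradicts the grid, which marks the three rows from screening to Week 24 and at early termination. That is weak. A footnote may narrow a row, and footnote h does so for joint counts and the physician's global assessment in PsO participants. Only the screening mark sits badly with a Week 0 restriction, and the case does not need it.

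The objection to any numerical claim also stands. The table above shows shortfalls of 6 points (0.60 × 0.10) to 45 points (0.90 × 0.50), but these reflect the values chosen. Moreover, f is the share caught multiplied by the share of those at sites that follow the footnote. If 60% of the subset were caught (assumed), f = 0.50 would need 0.50 / 0.60, or about 83%, of them to be at such sites.

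**Conclusion.** The point holds as an internal contradiction in the current text with a conditional consequence. Where a site follows footnote g literally, the Week 12 PASI 75 and sPGA (0,1) rates in Section 9.5.3(ii) are lowered or unchanged, never raised. The documents establish that direction and nothing about size. If no site follows the footnote, there is no bias.

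Two stronger readings are tempting and not supported. One is that the PsA skin summary will be off by a particular number of points; that would need p and f, and both are assumed here. The other is that Section 9.5.3(ii) is the only result at risk. It is the only one in the visible text, but further objectives and endpoints are redacted. The amendment summary shows that other efficacy endpoints include PASI, sPGA and BSA measures, with a note on PsA participants at or above 3% BSA. Those may be exposed too.

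The matter is worth correcting because lost assessments cannot be recovered and the correction is nearly free. It does not threaten the study's primary conclusion.

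**What to change.** Reword footnote g to agree with the closing note, Section 8.1, Table RHCZ.8.1 and Section 9.5.3:

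- PASI, BSA and sPGA at all study visits for PsO participants and for PsA participants with baseline BSA of psoriasis of at least 3%, including those who meet both disease definitions.
- For PsA participants below 3%, keep only the baseline assessment needed to classify them, consistent with the screening marks in the grid, and say that it serves classification. This keeps it in line with Table RHCZ.8.1, which lists no skin outcomes for that group.

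Send sites a clarification at the same time, since the wording affects data being collected.

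The cost is one reworded footnote and one communication to sites. No assessment is added beyond those already marked in the schedule, and no dose, visit or clinical rule changes.
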